11.1 Primary Efficacy Endpoint

11.1.1 Cumulative Number of Weeks of Platelet Response

Population: Full Analysis Set, Per Protocol Set

Target Phases: Core Phase

Analysis items:

- The cumulative number of weeks in which the platelet count is $\geq 50 \times 10^9/L$ during 26 weeks of treatment in the absence of rescue therapy for each subject

Contents:

- Descriptive statistics and 95% CI of mean of the cumulative number of weeks of platelet response during 26 weeks of treatment in the absence of rescue therapy is calculated.

Definitions:

- Platelet response: platelet count of $\geq 50 \times 10^9/L$

- Cumulative number of weeks of platelet response during 26 weeks of treatment in the absence of rescue therapy is calculated by the formula: (sum of platelet response duration)/7= sum of (last day platelet response - the first day platelet response +1)/7.
- All scheduled and unscheduled visits will be used. If the subject missed a visit, the visit date will be imputed based on analysis target date.
- Platelet response will be defined with consideration referring the handling of data as described in 3 cases below:
 - 1. Subjects who have missing platelet assessments at any scheduled visit of interest will be considered as non-responders at that time point.
 - 2. Subjects who use rescue therapy at any time during the 26-week treatment period will be considered as non-responders for all subsequent days after rescue therapy start date.
 - 3. Subjects who discontinue the study or who are lost to follow-up before 26 weeks will have all subsequent unobserved scheduled platelet assessments at the scheduled time points as having “missing” platelet values.

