#### 3 STUDY ENDPOINTS

# 3.1 Primary Efficacy Endpoint

In the Primary Investigation Phase (Core Phase), the primary efficacy endpoint is the cumulative number of weeks in which the platelet count is  $\geq 50 \times 10^9 / L$  during 26 weeks of treatment in the absence of rescue therapy.

Subjects using rescue therapy at any time during the 26-week treatment period will be considered not to have any platelet responses for all subsequent weeks after rescue therapy. A platelet response will be defined as a platelet count of  $\geq 50 \times 10^9/L$  and nonresponse will be defined as a platelet count  $< 50 \times 10^9/L$ . All analyses of platelet counts will be based on local laboratory results.

Missing platelet assessments at any given time point will be considered to be a nonresponse at that time point. Subjects who discontinue the study or who are lost to follow-up before 26 weeks will have all subsequent unobserved scheduled platelet assessments at the scheduled time points as having "missing" platelet values.

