# 4.3.3 Concomitant ITP Medication Reduction Period (Visits 8 to 13)

During this period, downward titration of concomitant ITP medication will be permitted in accordance with the guidelines described in Section 6.5.3. This may require additional study drug dose and dosage adjustments before and after the concomitant ITP medication downward titration. Subjects will return every 2 weeks during this period.

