8.6 Visit Windows

No formal visit windowing will be conducted, except assign appropriate visit per study day for the records of the End of Study visit (VISIT 22). Only scheduled visit assessment will be used in

the by visit analyses. If multiple records are found within the visit window, the record closest to target date will be used for analysis purposes.

All assessments will be used when calculating cumulative and maximum duration of platelet response. The visit target date will be used to impute the missing visit date.

All assessments during scheduled and unscheduled visits will be listed in the data listing and presented in individual subject figures.

| Analysis Visit | Analysis Window Target | Analysis Window Beginning Timepoint | Analysis Window Ending Timepoint |
|--------------------|------------------------|-------------------------------------|----------------------------------|
| Baseline | 1 day | - | 1 day |
| Visit 3 (Day 5) | 5 days | 2 days | 6 days |
| Visit 4 (Day 8) | 8 days | 7 days | 11 days |
| Visit 5 (Week 2) | 14 days | 12 days | 17 days |
| Visit 6 (Week 3) | 21 days | 18 days | 24 days |
| Visit 7 (Week 4) | 28 days | 25 days | 35 days |
| Visit 8 (Week 6) | 42 days | 36 days | 49 days |
| Visit 9 (Week 8) | 56 days | 50 days | 63 days |
| Visit 10 (Week 10) | 70 days | 64 days | 77 days |
| Visit 11 (Week 12) | 84 days | 78 days | 91 days |
| Visit 12 (Week 14) | 98 days | 92 days | 105 days |
| Visit 13 (Week 16) | 112 days | 106 days | 119 days |
| Visit 14 (Week 18) | 126 days | 120 days | 129 days |
| Visit 15 (Week 19) | 133 days | 130 days | 136 days |
| Visit 16 (Week 20) | 140 days | 137 days | 143 days |
| Visit 17 (Week 21) | 147 days | 144 days | 150 days |
| Visit 18 (Week 22) | 154 days | 151 days | 157 days |
| Visit 19 (Week 23) | 161 days | 158 days | 164 days |
| Visit 20 (Week 24) | 168 days | 165 days | 171 days |
| Visit 21 (Week 25) | 175 days | 172 days | 178 days |
| Visit 22 (Week 26) | 182 days | 179 days | 299 days |

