11.3.2 Maximum Duration (in weeks) of Platelet Response

| | |
|------------------|---|
| Population: | Full Analysis Set, Per Protocol Set |
| Target Phases: | Core Phase |
| Analysis items : | 
- Maximum duration (in weeks) of continuous platelet response |
| Contents: | 
- Descriptive statistics of Maximum duration (in weeks) of continuous platelet response for each subject is calculated. |
| Definitions: | 
- Maximum duration (in weeks): The maximum value of the platelet response durations (in weeks) is the longest platelet response duration.- For platelet response duration and the handling of data refer to table 11.1.1 Cumulative Number of Weeks of Platelet Response |

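### Read literally, the primary-endpoint formula in SAP 11.1.1 counts a response run only from its first to its last responding visit, so interrupted responders score fewer weeks than the protocol endpoint implies

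*SAP*

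**What the plan says.** Protocol 3.1 defines the primary endpoint as "the cumulative number of weeks in which the platelet count is" at or above 50 × 10⁹/L during 26 weeks of treatment without rescue therapy.

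SAP 11.1.1 turns this into days divided by 7: "sum of (last day platelet response - the first day platelet response +1)/7". It adds: "All scheduled and unscheduled visits will be used. If the subject missed a visit, the visit date will be imputed based on analysis target date". A missed count is a nonresponse: "Subjects who have missing platelet assessments at any scheduled visit of interest will be considered as non-responders at that time point". SAP 8.6 repeats that "All assessments will be used when calculating cumulative and maximum duration of platelet response".

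SAP 11.3.2 borrows the same construction ("For platelet response duration and the handling of data refer to table" 11.1.1). It also shows that one subject can have several durations: "The maximum value of the platelet response durations (in weeks) is the longest platelet response duration".

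The visit grid is uneven. Counts fall on Days 5, 8, 14, 21 and 28. From Week 6 to Week 16, "Subjects will return every 2 weeks during this period" (Protocol 4.3.3). From Week 18 to Week 26 visits are weekly. Protocol 4.3.4 adds weekly visits for 3 consecutive weeks after a dose adjustment, a reduction of concomitant ITP medication, or rescue.

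Neither document states how long a responding count is taken to last, on what day a run closes, or what a single isolated response is worth.

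**The concern.** Only assessment days carry a platelet count. If the first and last response days are the first and last responding visits of a run, the interval after the last responding visit earns nothing. The score then depends on three things besides time in response: how often the count crosses 50, how far apart the visits are, and whether a visit was missed. Two subjects with the same platelet course can receive different primary outcomes.

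This is the only confirmatory measure, and its mean is judged by whether the lower 95% confidence limit reaches 8.02 weeks. The planning assumptions leave almost no room, so a modest scoring artefact could decide the result.

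**Working it through.** **Inputs.** Mean 12.0, SD 8.75, n = 19, hurdle 8.02 (Protocol 10.2.5, SAP 6). t-based interval for a mean (SAP Appendix 1). Target days 5, 8, 14, 21, 28, then every 14 days from 42 to 126, then every 7 days to 182 (SAP 8.6).

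**1. The plan's own figure.** n = (1.96 × 8.75 / (12.0 − 8.02))² = 18.57, rounded up to 19. This reproduces the stated size. At n = 19 the expected lower limit is 12.0 − 1.96 × 8.75/√19 = 8.07 with z, and 7.78 with t on 18 degrees of freedom.

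**2. Loss per run.** Literal score of a run: last − first + 1 days. Crediting each response up to the day before the next nonresponding or missed visit: next − first days. The difference is (next − last) − 1, that is 7 − 1 = 6 days (0.86 week) on a weekly gap and 14 − 1 = 13 days (1.86 weeks) on a 2-weekly gap.

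**3. Patterns on the target days (weeks).**

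| Pattern | Literal | Credit to next visit |
|---|---|---|
| Isolated response, Week 20 | 1/7 = 0.14 | 7/7 = 1.00 |
| Isolated response, Week 10 | 1/7 = 0.14 | 14/7 = 2.00 |
| Isolated responses, Weeks 6, 10 and 14 | 3/7 = 0.43 | 42/7 = 6.00 |
| Alternating visits from Day 8 | 10/7 = 1.43 | 84/7 = 12.00 |
| Two on, one off from Day 8 | 9.86 | 17.00 |
| Three on, one off from Day 8 | 14.57 | 19.00 |
| Continuous, Day 8 to Day 182 | 175/7 = 25.00 | 175/7 = 25.00 |
| Same, Week 10 visit missed | (49 + 99)/7 = 21.14 | (62 + 99)/7 = 23.00 |

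The missed visit costs 25.00 − 21.14 = 3.86 weeks literally, against 25.00 − 23.00 = 2.00 weeks.

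**4. Dependence on the grid.** Suppose a subject is truly in response on Days 60 to 80 (21 days, 3.0 weeks). On scheduled visits only Day 70 responds: 0.14 week. With extra weekly visits on Days 63 and 77, the literal score is (77 − 63 + 1)/7 = 2.14 weeks. Crediting to the next visit gives 14/7 = 2.0 and 21/7 = 3.0 weeks, so it still varies with the grid, but less.

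**5. What a lower mean does.** The chance that the lower t-limit reaches 8.02 at n = 19 and SD 8.75 (noncentral t) is 46.7% at a mean of 12.0. It is 37.5%, 29.0%, 15.3% and 6.7% if scoring lowers the mean by 0.5, 1, 2 and 3 weeks.

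**6. Plausible size.** This is an illustrative simulation of 20,000 subjects per setting on scheduled visits only. Each subject has an own response rate from a beta distribution, and week-to-week persistence (ρ) is varied; these patterns are assumptions. The settings whose spread comes closest to 8.75 are:

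| Beta parameters, ρ | SD (credit to next visit) | Mean, credit to next visit | Mean, literal | Shortfall |
|---|---|---|---|---|
| 0.55/0.6, ρ = 0 | 8.99 | 12.17 | 9.18 | 2.99 |
| 0.55/0.6, ρ = 0.3 | 9.05 | 12.10 | 9.64 | 2.46 |
| 0.55/0.6, ρ = 0.6 | 9.43 | 12.24 | 10.66 | 1.58 |
| 1.2/1.4, ρ = 0.8 | 8.90 | 11.68 | 10.52 | 1.16 |

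Across all ten settings run, the shortfall was 0.46 to 4.07 weeks. The largest values came with an SD of 7.2 to 7.3 and the smallest with an SD of 10.0 or more.

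**The case against.** The strongest reply is that the literal reading is not forced. The SAP does not say that the last response day is a visit day. If it means the day before the next nonresponse, the same formula gives 83 − 70 + 1 = 14 days for an isolated Week 10 response, with no loss. Imputing a date for a missed visit fits that reading, because such a date is needed to close a run; on the literal reading it serves at most for ordering. This stands: the defect can be called an undefined term. But a programmer following the printed words could equally implement the literal version, and the two differ materially.

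Second, the starkest patterns assume a bare 14-day grid. Under Table 2 of the protocol, a count below 50 after at least 2 weeks of treatment leads to a dose change, which triggers weekly visits that all enter the score. This stands too. It shrinks the loss but does not remove it, since each run still loses 6 days on weekly visits.

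Third, the benchmarks may have been scored in the same way. The design is meant to replicate Study 302, and that study's median of 12.4 weeks suggests a day-based score, though it does not reveal the run-end rule. If the rule was the same, the comparison with 8.02 is on one scale. A reader might infer that the hurdle and the result are mismatched; the documents do not say how Study 302 or TRA108109 was scored, so that is not shown.

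Fourth, the bias is conservative. That is correct: it raises the risk of missing the hurdle, not of false success.

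**Conclusion.** The point holds for the formula taken literally. That score departs from weeks with a count of at least 50 × 10⁹/L, and it depends on visit spacing and on the number of interruptions. Uninterrupted responders are unaffected. With a between-subject spread like the one the plan assumes, the mean falls by about 1 to 3 weeks. That range rests on assumed response patterns and scheduled visits only, and the extra weekly visits would reduce it.

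A reader might go further and infer that a drug delivering 12 response weeks would be recorded as 8 to 9. The planning figures do not support that. Such values arise when every subject is given the same 50% response process, which yields an SD of about 3.4 to 6.8 weeks against the assumed 8.75. An SD of 8.75 around 12 on a 26-week scale implies many subjects near zero or near continuous response, whom the formula barely touches.

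The matter still needs settling, because at the planning values the lower limit clears 8.02 by only about 0.05 week with z and misses it by about 0.24 week with t.

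**What to change.** In SAP 11.1.1, and so by reference in 11.3.2, define the last day of a response run as the day before the next nonresponding assessment or the imputed date of a missed visit. Cap it at Week 26 and at the start of rescue therapy. An isolated response then counts for its own visit interval. If Study 302 or TRA108109 is known to use another run-end rule, use that rule for the comparison with 8.02 and say so. Report whichever rule is not primary as a sensitivity analysis.

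The cost is a few lines of SAP text and a small programming change, with no new data; SAP section 2 has the plan finalized before Core Phase database lock. The downside is that response is assumed to persist until the next visit, up to 13 unobserved days on the 2-weekly grid, which raises the score. In an open-label, single-arm study that is a reason to fix the rule in writing before the endpoint is derived and to show both versions.

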11.1.2 Cumulative Number of Weeks of Platelet Response by Subgroups

Population: Full Analysis Set, Per Protocol Set, Safety Set

Target Phases: Core Phase

Analysis items: - The cumulative number of weeks in which the platelet count is $\geq 50 \times 10^9/L$ during 26 weeks of treatment in the absence of rescue therapy

Contents: - Conduct a subgroup analysis for “[11.1.1 Cumulative Number of Weeks of Platelet Response](#)”. Planned subgroups are defined below:

- Sex (Male, Female)
- Age (<65 yrs, ≥ 65 yrs)
- Baseline platelet count ($\leq 15 \times 10^9/L$, $> 15 \times 10^9/L$)
- Use of concomitant ITP medications (Yes, No)
- Splenectomy status (Yes, No)
- Baseline creatinine clearance (30 \leq - <60 mL/min, 60 \leq - <90 mL/min, ≥ 90 mL/min, Missing (if any))

11.2 Key Secondary Efficacy Endpoint

11.2.1 Platelet Response Rate at Visit 4 (Day 8)

Population: Full Analysis Set, Per Protocol Set

Target Phases: Core Phase

Analysis items: - Platelet response rate at Visit 4 (Day 8)

Contents: - The number of platelet response (Yes/No) at Visit 4 (Day 8) and its proportion with 95% CI is calculated.

Definitions: - Responders (Yes): Subjects with a platelet count $\geq 50 \times 10^9 / L$ at Visit 4 (Day 8) in the absence of rescue therapy before or on Visit 4 (Day 8).
- Non-responders (No): Subjects with a platelet count $< 50 \times 10^9 / L$ at Visit 4 (Day 8) or with missing platelet counts at Visit 4 (Day 8) or use of a rescue therapy before or on Visit 4 (Day 8).

- Regarding the efficacy data handling, refer to 3 cases below:

- 1. Subjects who have missing platelet assessments at Visit 4 (Day 8) will be considered as non-responders.
- 2. Subjects who use rescue therapy before or on Visit 4 (Day 8) will be considered as non-responders at Visit 4 (Day 8).
- 3. Subjects who discontinue the study or who are lost to follow-up before or on Visit 4 (Day 8) will be considered as non-responders at Visit 4 (Day 8).

- Regarding 95% CI for binomial proportions, refer to [8.3.2 Proportion and Confidence Intervals for proportions](#)

11.3 Other Efficacy Endpoints

11.3.1 Durable Platelet Response

Population: Full Analysis Set, Per Protocol Set

Target Phases: Core Phase

Analysis items: - Durable platelet response

Contents: - The number of responders/non-responders and its proportion with 95% CI is calculated.

Definitions: - Responders (Yes): Subjects who have at least 6 of 8 (i.e., $\geq 75\%$) weekly platelet counts $\geq 50 \times 10^9 / L$ during the last 8 weeks (from Visit 15 (Week 19) to Visit 22 (Week 26)) of treatment over the 26-week treatment period and not taking any rescue therapy.
- Non-responders (No): Subjects who have less than 6 weekly platelet counts $\geq 50 \times 10^9 / L$ during the last 8 weeks over the 26-week treatment

- period or taking any rescue therapy.
- Regarding the data handling:
 - 1. Subjects who have missing platelet assessments at scheduled visits of interest will be considered as non-responder at any given time point.
 - 2. Subjects who use rescue therapy at any time during 26-week treatment period will be considered as non-responders for all subsequent days after rescue therapy start date.
 - 3. Subjects who discontinue the study or who are lost to follow-up before 26 weeks will have all subsequent unobserved scheduled platelet assessments at the scheduled time points as having “missing” platelet values.
- Regarding 95% CI for binomial proportions, refer to [8.3.2 Proportion and Confidence Intervals for proportions](#).
- Regarding Rescue therapy, refer to table [11.3.9 Subjects with any Rescue Therapy Use](#)

11.3.2 Maximum Duration (in weeks) of Platelet Response

| | |
|------------------|---|
| Population: | Full Analysis Set, Per Protocol Set |
| Target Phases: | Core Phase |
| Analysis items : | 
- Maximum duration (in weeks) of continuous platelet response |
| Contents: | 
- Descriptive statistics of Maximum duration (in weeks) of continuous platelet response for each subject is calculated. |
| Definitions: | 
- Maximum duration (in weeks): The maximum value of the platelet response durations (in weeks) is the longest platelet response duration.- For platelet response duration and the handling of data refer to table 11.1.1 Cumulative Number of Weeks of Platelet Response |

11.3.3 Platelet Count ($10^9/L$) and Change from Baseline by Visit

| | |
|-----------------|---|
| Population: | Full Analysis Set, Per Protocol Set (for Core Phase only) |
| Target Phases: | Core Phase, Extension Phase |
| Visits: | 
- Core Phase: Baseline - Visit 22 (Week 26)- Extension Phase: E 1 (Month 1) - Last Visit |
| Analysis items: | 
- Measured value and change from baseline for platelet count |
| Contents: | 
- Summary statistics of platelet count from local laboratories for all subjects in each visit are calculated. |

11.3.4 Median (Q1, Q3) Platelet Count ($10^9/L$) of Local Platelet Count Over Treatment Period

| | |
|-----------------|--|
| Population: | Full Analysis Set, Per Protocol Set (for Core Phase only) |
| Target Phases: | Core Phase, Extension Phase |
| Visits: | 
- Core Phase: Baseline - Visit 22 (Week 26)- Extension Phase: E 1 (Month 1) - Last Visit |
| Analysis items: | 
- Median, Q1, and Q3 values of measured values and change from baseline values |
| Contents: | 
- Series plot for median (Q1, Q3) platelet count from local laboratories will be presented graphically by visit. |

11.3.5 Platelet Count ($10^9/L$) of Individual Subjects

| | |
|-----------------|---|
| Population: | Full Analysis Set |
| Target Phases: | 
- Core Phase |
| Analysis items: | 
- Measured value for platelet count |
| Contents: | 
- Spaghetti plot for platelet count from local laboratories will be presented graphically by subject. |

11.3.6 Platelet Response by Visit

| | |
|-----------------|--|
| Population: | Full Analysis Set, Per Protocol Set |
| Target Phases: | Core Phase |
| Visit: | Visit 3 (Day 5) - Visit 22 (Week 26) |
| Analysis items: | 
- Platelet Response by Visit |
| Contents: | 
- The number of subjects with platelet response (Yes/No) at each analysis visit are calculated based on subjects with assessment available at the visit (n). |
| Definitions: | 
- Responders (Yes): Subjects who have platelet count $\geq 50 \times 10^9/L$ and in the absence of rescue therapy.- Non-responders (No): Subjects who have platelet count $< 50 \times 10^9/L$ or have platelet count $\geq 50 \times 10^9/L$ that occurs within 8 weeks after rescue therapy usage.- Regarding the efficacy data handling, refer to the case below:
➤ 1. Subjects who have missing platelet assessments will be excluded from the summary at that visit. |

- 2. If subjects use rescue medication, subjects will be considered as non-responders from the rescue medication start date to rescue medication end date + 8 weeks.
- The denominator to calculate the proportion is the number of subjects in target population by each analysis visit with non-missing data.

11.3.7 Complete Platelet Response Rate by International Working Group (IWG) by Visit

| | |
|-----------------|---|
| Population: | Full Analysis Set, Per Protocol Set |
| Target Phases: | Core Phase |
| Visits: | Visit 3 (Day 5) - Visit 22 (Week 26) |
| Analysis items: | 
- Complete platelet response by IWG |
| Contents: | 
- The number and proportion of subjects with a complete platelet response (Yes/No) at each analysis visit are calculated based on subjects with assessment available at the visit (n). |
| Definitions: | 
- Complete platelet response:
➤ Responders (Yes): Subjects with a platelet count $\geq 100 \times 10^9/L$ and in the absence of bleeding or rescue therapy.➤ Non-responders (No): Subjects with a platelet count $< 100 \times 10^9/L$ or the presence of bleeding. Platelet assessment with any bleeding event at the same visit or a platelet count that occurs within 8 weeks after rescue therapy is considered as nonresponse.- Regarding the efficacy data handling, refer to the cases below:
➤ 1. Subjects who have missing platelet assessments will be excluded from the summary at that visit.➤ 2. If subjects use rescue medication, subjects will be considered as non-responders from the rescue medication start date to rescue medication end date + 8 weeks.➤ 3. Subject who has WHO bleeding scale grade ≥ 1 will be considered as non-responder at that visit.- The denominator to calculate the proportion is the number of subjects in target population by each analysis visit with non-missing data. |

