### 4.3.4 Maintenance Period (Visits 14 to 22)

Subjects will continue treatment in order to maintain platelet counts of  $\geq 50 \times 10^9 / L$  and  $\leq 200 \times 10^9 / L$ . Study drug dose and dosage adjustments will be made in accordance with the dose and dosage titration guidelines. No downward titration of concomitant ITP medication will be permitted during this period unless there is a safety concern. Subjects will return weekly for visits.

At the EOT Visit (Visit 22), subjects will have the option to enter the Extension Phase and continue to receive avatrombopag. Subjects who are unable or unwilling to continue in the Extension Phase of the study will enter the Dose/dosage tapering and Follow-up Periods.

Subjects who require study drug dose adjustments, who undergo concomitant ITP medication reduction or who receive rescue therapy during the periods of Concomitant Medication Reduction and Maintenance Periods are required to return for weekly visits for 3 consecutive weeks.

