## 7.2.8 Unscheduled Visit

The Unscheduled Visit details the minimum assessments required for those subjects who need an Unscheduled Visit for dose titration or additional platelet count blood draws, however, additional assessments may be performed as needed based on other reasons for an Unscheduled Visit.

- Collect vital signs (blood pressure and pulse) at each visit. Vital signs should be taken after sitting for 5 minutes whenever possible. Vital signs should be taken prior to any blood draws.
- Collect platelet counts via local lab.
- Perform WHO Bleeding Scale Assessment (Appendix C) at each visit. The Investigator should ask the subject the following question: "Have you experienced any bruising or bleeding since the last visit?"
- Review and record AEs that may have occurred since the last visit.
- Record concomitant medications and procedures since the last visit.

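### A resolved, non-rescued bleed recorded at an unscheduled visit is not counted in the IWG response tables, because bleeding is scored only at the scheduled visit

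*SAP*

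**What the plan says.** SAP 11.3.7 (complete response) and SAP 11.3.8 (response) are tabulated by visit over scheduled Visits 3 to 22, and both require that the subject is not bleeding. Section 11.3.7 lists as nonresponse a "Platelet assessment with any bleeding event at the same visit". Its data-handling rule adds that a subject with WHO grade 1 or higher "will be considered as non-responder at that visit". Section 11.3.8 repeats the first rule and refers back to 11.3.7 for the handling.

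On which records count, SAP 8.6 says "Only scheduled visit assessment will be used in" the by-visit analyses, and "If multiple records are found within the visit window, the record closest to target date will be used for analysis purposes". It makes one exception: "All assessments will be used when calculating cumulative and maximum duration of platelet response". Neither the IWG endpoints nor the WHO scale are named in that exception.

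Under Protocol 8.2, every WHO grade after baseline rests on the question "Have you experienced any bruising or bleeding since the last visit". Protocol 7.2.8 requires the same question at unscheduled visits. Under Protocol 4.3.4, subjects with a study drug dose adjustment, a reduction of ITP medication or rescue therapy "are required to return for weekly visits for 3 consecutive weeks". Protocol 7.2.3 handles additional visits in the bi-weekly period as unscheduled visits.

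**The concern.** The bleeding question looks back over an interval, and each visit of any kind restarts that interval. The IWG tables then discard the answers given at unscheduled visits. Two subjects with the same bleed and the same platelet counts can therefore be classified differently only because one of them had an extra visit. At stake is whether the bleeding component of the two IWG endpoints means the same thing for subjects with and without extra visits, and whether the reported rates are somewhat too high.

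**Working it through.** The plan states no figure on this point, so there is nothing to reproduce. The check traces the rules and uses the target days in SAP 8.6.

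1. **Intervals.** The target days are 1, 5, 8, 14, 21, 28, 42, 56, 70, 84, 98, 112, 126, and then every 7 days to 182. The differences are 4, 3, 6, 7, 7, then 14 seven times, then 7 eight times. That is 5 + 7 + 8 = 20 intervals. Seven of them (Week 4 to Week 18) last 14 days, which is 7 × 14 = 98 of 182 − 1 = 181 days.

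2. **Same bleed, with and without an extra visit.** Take an illustrative bleed between Day 56 and Day 63 that resolves before Day 63, with no rescue and a count of at least 100 × 10⁹/L on Day 70.
   - No extra visit: on Day 70 the question covers 70 − 56 = 14 days. The bleed is reported, the WHO grade is 1 or higher, and Visit 10 is a nonresponse.
   - Unscheduled visit on Day 63: the bleed is graded there. On Day 70 the question covers 70 − 63 = 7 days and the grade is 0. The Day 63 record is not used, so Visit 10 is a complete response. The look-back lost is 7/14 = 50%.

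3. **The visit windows do not rescue the record.** Suppose unscheduled records were admitted. Day 63 lies in the Visit 9 window (Days 50 to 63), where the record closest to Day 56 is kept. A scheduled record on Day 56 is 0 days from target and the unscheduled one is 7 days away, so the latter is dropped. Even if it were kept, it would count at Visit 9 and not at Visit 10.

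4. **Comparable events have a rule.** For rescue, 11.3.7 extends nonresponse to 8 weeks after the end of rescue. For platelet duration, 8.6 uses all assessments. Bleeding has neither.

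5. **What has to coincide.** A classification changes only if the bleed is recorded at an unscheduled visit, has resolved by the next scheduled visit, did not lead to rescue, and the subject meets the platelet criterion at that scheduled visit.

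6. **Size per subject.** With 19 subjects, all with data at the visit, one reclassified subject is 1/19 = 5.3 percentage points, two are 2/19 = 10.5 and three are 3/19 = 15.8. The number of such subjects cannot be derived, because the documents give no rate of bleeds of this kind.

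**The case against.** The strongest reply is that the SAP deliberately defines a status at a visit, and a subject with a high count and no bleeding at Week 10 meets it. This stands only in part. The grade is not a snapshot: without an extra visit, a bleed that ended days earlier still makes Week 10 a nonresponse. The definition is already interval-based, and the visit pattern sets the length of the interval. Sites could also read the question as reaching back to the last scheduled visit, which would close the gap, but the protocol does not say so.

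Other parts of the reply stand, and they rule out stronger readings that a reader might infer:

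- **That the loss falls on the subjects most likely to bleed.** This is not shown. Rescued subjects are covered by the 8-week rule. Under Protocol 6.5.3, reduction of ITP medication is considered only at counts that remain above 200 × 10⁹/L. Under Protocol 6.4.4, dose adjustments include decreases for high counts.
- **That the bleed vanishes from the study.** It stays in the listings. On the plain wording of SAP 11.3.11, which is not a by-visit analysis, it also stays in the worst post-baseline grade. A bleed still present at the next scheduled visit is counted in the IWG tables as well.
- **That the size can be estimated.** With an assumed constant daily chance q of a bleed, the chance of at least one is 1 − (1 − q)¹⁴ over 14 days and 1 − (1 − q)⁷ over 7 days. This gives 6.8% and 3.4% at q = 0.5%, 13.1% and 6.8% at 1%, and 24.6% and 13.2% at 2%. The figures show that look-back length matters. They do not measure inflation, because q is assumed and the calculation ignores the conditions in step 5.
- **That response will appear to improve at Week 19.** The look-back does fall from 14 to 7 days there, but the effect depends on an unknown bleeding rate. SAP 8.3.5 plans no testing unless otherwise noted, and no trend statement is specified.

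**Conclusion.** The gap is real and narrow. As written, the IWG tables omit resolved, non-rescued bleeds recorded at unscheduled visits, mainly between the bi-weekly visits from Week 4 to Week 18. The same bleed without the extra visit would count. The direction is certain: omitting bleeds can only raise the IWG rates. Each affected subject is worth 5.3 points at a visit if all 19 have data, and the expected total is unknown.

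The conclusion assumes that sites ask the question as printed, so that an unscheduled visit restarts the recall period. The IWG responses are descriptive endpoints outside the primary and key secondary endpoints, neither of which uses bleeding. This is a low-cost correction to make before the Core Phase database lock, not a threat to the main result.

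**What to change.** In SAP 11.3.7 and 11.3.8, define bleeding at a visit as the highest WHO grade recorded at any scheduled or unscheduled assessment after the previous scheduled visit, up to and including the current one. In SAP 8.6, except this use of the WHO grade from the scheduled-only rule and from the closest-record rule. The platelet count can still be taken from the scheduled visit.

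The cost is one sentence in each section, a small programming change and possibly slightly lower IWG rates. No new data are needed, since Protocol 7.2.8 already requires the WHO assessment at unscheduled visits.

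Optionally, note under the tables that the look-back length varies across all scheduled visits: 3 to 7 days at Visits 3 to 7, 14 days at Weeks 6 to 18, and 7 days at Weeks 19 to 26. The fix does not remove that difference. It removes only the dependence on extra visits.
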